3.2.2 Secondary Outcome Measures

A secondary outcome of the study will be reviewing the volume and pressure measurements from the barostat device. The surveys will also be reviewed to see if the study participants have a change in their symptoms.

4 Study Design

This is a placebo-controlled trial. The placebo is the sham-TEA visit. The study will recruit 25 study participants with IBS-C. These study participants will be recruited from the UM Health Research Recruiting Registry (UM HealthResearch.org), Michigan Bowel Control Program (MBCP), Functional Bowel Disease (FBD), and the study team will screen the gastroenterology clinic schedules via MiChart.

This is a phase 1 trial. This study will only occur at the University of Michigan. There is only one group/arm of study participants. The study team plans to complete enrollment within 12 months of beginning to the study. Study participant participation will be at a minimum 5 weeks (1 week between

visits) and at a maximum 15 weeks (3 weeks between each visit). The test agent is the novel TEA device.

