3.2.1 Primary Outcome Measures

The barostat device will measure the volume changes in the rectum during controlled distension of the gastrointestinal organs. If the TEA is successful, the study participant's maximum tolerance should increase after TEA compared to their first maximum tolerance of the visit. This will be defined by comparing their maximum tolerance pre and post TEA.

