4.1 Schedule of Events for Each Visit

Every visit is the same and will follow the steps detailed below, with the exception of the first visit which will include the informed consent process. At visit one, the study team will randomly generate the stimulations schedule unique to each study participant; this is the order of locations and currents by using a random generator. For example, ST36-100Hz, ST36-25Hz, PC6-100Hz, PC6-25Hz and Sham-TEA.

48 Hours prior to the visit: The study participants will not take any medications known to affect the gut or pain perception.

8:00 pm on the night before the visit: The study participants begin fasting for their visit the next day. Study participants can still drink water. Study participants cannot drink coffee, tea, juices or eat any food items.

Day of the Visit:

Study participants will come to the study location, the Gastrointestinal Physiology Lab in University of Michigan. The visit will take place in one of the private rooms within the lab. **If the study participant is a women of child bearing potential:** She will complete a pregnancy test provided by the study team. If her pregnancy test is positive, she will be excluded from further participation in the study and will not complete the visit.

Rome IV Criteria for Irritable Bowel Syndrome: Upon arrival for every visit, the study participant will complete the Rome IV Criteria for Irritable Bowel Syndrome survey.

Enema: The study participant will be given a rectal enema to clean the rectum. Then the study participant will undress from the bottom down and be given a gown and sheets for comfort and privacy.

Position the study participant: The study participant will be asked to lie down on the medical examination table on one side and bring his or her knees up to the chest, similar to the fetal position. The table has rails that will protect the study participant from falling. The staff may use pillows to adjust and secure the study participant as well as for comfort.

Electrode Placement: The GI physiology laboratory staff will place two electrocardiogram (ECG) electrodes from of the TEA device on the subject's skin, one on the wrists at location PC6 and the other

Fig.1: Locations of PC6 and ST36.

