on upper leg below the knee at location ST36. These two electrodes will be used for delivering weak electrical current stimulation. The electric current and stimulating electrode location is determined by that study participant's randomized stimulation schedule. Electrodes will be placed at both locations at each visit.

An additional three ECG electrodes connected to the ECG machine will be placed on the study participant's skin, one on the manubrium of sternum, one above the breastbone and one on the study participant's right chest. These three electrodes will be used for recording the ECG. Before the placement of each of the 5 electrodes, the skin area where the electrodes to be placed will be carefully cleaned using skin-prep materials.

[figure not shown]

Fig.2: Locations of ECG electrodes to read electrocardiogram.

Baseline data collection with the Barostat:

The Barostat is an FDA-Approved device that measures pressure in the rectum. The device has a thin and flexible polyvinyl catheter (PVC) will be placed 5-15 cm into the study participant's rectum. Once placed, this catheter will be in the rectum for the remainder of the visit.

Rest - 15 Minutes

While the study participant is at rest, baseline data will be collected for 15 minutes.

Inflation with the Barostat:

The GI physiology lab staff will inflate a small balloon at the tip of the catheter and ask the study participant to assess the sensation. During this period, the study participant will be asked to take a note of their first sensation, urge to defecate and maximum tolerance; meanwhile, the study participant will also be asked to report the scale of pain or discomfort during the process of the balloon distention. The study participant will complete the Visual analog Scale Pain Score during inflation.

Maximum Tolerance:

Once the maximum tolerance is reached, the inflation will stop and the air will be removed.

TEA – 15 minutes

One of the randomly assigned TEA methods (or sham-TEA) will be performed for 15 minutes.

Inflation with the Barostat and TEA:

Then the inflation process described above will be repeated while applying the TEA. The study participant may sense the weak electrical stimulation. If the stimulation intensity is uncomfortable for the study participant, the stimulation will be set a level where the study participant feels comfortable. This will be noted in the visit summary. The study participant will complete the Visual Analog Scale Pain Score during inflation.

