10.3 Final Analysis Plan

Analysis of variance (ANOVA) will be performed to investigate the difference in each of the outcomes among different sessions. Tukey's test will be used for study the differences in each of the measurements between two stimulation points (same stimulation parameters) and between two stimulation parameter sets (same stimulation points). The Pearson correlation analysis will also be performed to investigate the correlation between each of autonomic function parameters and the pain score or sensation threshold.

11 Source Documents and Access to Source Data/Documents

Only members of the study team will have access to source data. This includes: all information, original records of clinical findings, observations, or other activities in a clinical trial necessary for the reconstruction and evaluation of the trial.

12 Quality Control and Quality Assurance

- The study team will be present for each visit and follow the visit CRFs. The study team will go through the procedures with the GI physiology lab staff members to ensure that there is adherence to the protocol.
- The study team will sign the bottom of each study CRF at the end of the visit.

13 Ethics/Protection of Human Study participants

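### The trial is called placebo-controlled, but no masking and no sham content are described, and one staff group performs TEA and elicits the self-reported outcome, so active versus sham is open to expectation bias

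*Combined protocol and SAP*

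**What the plan says.** - **Control.** Section 4 (Study Design): "This is a placebo-controlled trial. The placebo is the sham-TEA visit". No section says what current, site or sensation a sham visit involves.
- **Outcome.** Section 3.2.1 bases success on a rise in maximum tolerance within the visit: "This will be defined by comparing their maximum tolerance pre and post TEA".
- **How it is obtained.** Section 4.1: "The GI physiology lab staff will inflate a small balloon at the tip of the catheter and ask the study participant to assess the sensation". In the same step, "the study participant will be asked to take a note of their first sensation, urge to defecate and maximum tolerance". The participant also completes the VAS pain score during each inflation.
- **Who does what.** Section 4.1: "The GI physiology laboratory staff will place two electrocardiogram (ECG) electrodes from of the TEA device". The précis in the Protocol Summary has the same lab staff performing TEA.
- **Timing.** The second inflation in 4.1 takes place with TEA running: "The study participant may sense the weak electrical stimulation". Intensity may be lowered for comfort at that point.
- **Order.** The study team generates each participant's full five-visit order, at visit one according to 4.1 and before the first visit according to 5.4.1. No concealment of the order is described.
- **Others present.** Section 12: "The study team will be present for each visit and follow the visit CRFs".
- **Existing safeguard.** Electrodes go on both sites at every visit (4.1).

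**The concern.** Maximum tolerance and VAS pain are the participant's own judgements, given in response to staff prompts. A sham session controls for expectation only if participant and assessor cannot readily tell it from an active one. Here the staff group that performs TEA also asks for the thresholds, the current can be felt, and comfort may be discussed during the inflation that yields the post-TEA value. Nothing says how any of this is handled at a sham visit. If expectation raises reported tolerance at active visits, a difference from sham can appear without any TEA effect.

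This matters even in a pilot. Section 3.1 asks which combination, if any, reduces pain most, and Section 10.2 counts the placebo among the methods compared. The part of that question covered by the words 'if any' depends on a credible sham.

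**Working it through.** **The plan's own figure.** Section 10.2 allows 20% dropout and needs 20 completers: 20 / (1 − 0.20) = 25, which matches the stated enrolment. The 20 cannot be derived, because no effect size, SD, level or power is given. The calculation below is therefore an illustration under assumptions.

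**Inputs**
- n = 20 completers (10.2) and k = 5 conditions (5.4.1).
- Analysis: ANOVA across sessions, with Tukey's test (10 and 10.3).
- Assumed: 5% level (none is stated), no true TEA effect, independent residuals with SD σ within participant, and expectation bias b·σ added equally to the four active sessions, with b = 0.2, 0.3 or 0.5.

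**Five-session ANOVA.** Degrees of freedom are 4 and (20 − 1)(5 − 1) = 76; the critical F is 2.49. The mean of the five sessions is 0.8b, so each active session deviates by 0.2b and sham by −0.8b. The squared deviations sum to 4(0.2b)² + (0.8b)² = 0.8b². The noncentrality is λ = 20 × 0.8b² = 16b².

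**Tukey, at least one active session above sham.** The critical studentized range (5 means, 76 df) is 3.95, so the honest significant difference is 3.95/√20 = 0.88 residual SD. Rates come from 200,000 simulated trials per row.

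| b | λ = 16b² | ANOVA falsely positive (noncentral F) | Tukey: any active above sham |
|---|---|---|---|
| 0 | 0 | 5.0% | 1.2% |
| 0.2 | 0.64 | 8.2% | 5.6% |
| 0.3 | 1.44 | 12.8% | 10.7% |
| 0.5 | 4.00 | 30.2% | 29.6% |

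A separate simulation of 20,000 trials gave 8.5%, 12.4% and 30.5% for the ANOVA and 5.8%, 10.5% and 30.0% for Tukey, which agrees within simulation error.

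**Between active modalities.** With equal bias, the chance of a false active-versus-active Tukey difference stays at about 3% for every b, and each modality ranks first about 25% of the time. Equal bias cancels here.

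**Do the existing features help?** Electrodes at both sites hide placement. They do not hide whether or where current is felt, or the setting from whoever operates the device. Random order balances period effects. The within-visit baseline removes differences between days. Expectation about the assigned stimulation acts after that baseline, so none of the three removes it.

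**The case against.** The strongest reply is that this is a pilot. Sections 10.2 and 10.2.2 say efficacy is not assessed, and the Tukey contrasts named in 10 and 10.3 are between sites and between frequencies, where equal bias cancels. Section 10 also speaks of four sessions. If those are the active ones, sham is outside that ANOVA and its error rate stays at about 5%. This stands as a limit on what is affected. It does not dispose of the point, because the trial is still described as placebo-controlled and the objective still allows that no combination works.

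A reader might infer more than the documents support:
- **That the trial is unmasked or open-label.** The documents are silent; they never say so. What participants are told about sham may be in the consent form, which is not available here, so that part cannot be judged.
- **That one individual does everything.** The overlap is shown for the lab staff as a group only.
- **That the operator can end inflation early or push further.** Section 4.1 stops inflation at maximum tolerance, which the participant notes.
- **That the modality taken forward would be chosen on bias.** This needs expectation to differ between modalities. It could, since participants may feel which site is active, but that was not modelled.
- **That false positives reach 22% or 51%.** A pooled active-versus-sham test would give about 12.5%, 22.1% and 50.7% at the three bias levels, but no such test is planned.

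The ECG-derived autonomic outcomes (10.2.2) are not self-reported and are less exposed.

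**Conclusion.** The point holds for the active-versus-sham comparison. The protocol describes neither masking nor the sham, and it gives stimulation and outcome elicitation to the same staff group, so carrying it out as written leaves that comparison open to expectation bias. Under the stated assumptions, a bias of 0.2 to 0.5 within-participant SD raises the five-session ANOVA's false-positive rate from 5% to between about 8% and 30%. It raises the chance that Tukey's test shows an active session above sham from about 1% to between about 6% and 30%. The size of the bias is an assumption, since the documents give no SD or prior data, and the figures apply only if sham enters the analysis. The plan should be changed, but the comparisons among the four active modalities are not shown to be invalid.

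**What to change.** Amend 4.1 and 5.4.1, and reconcile them with the précis, which has lab staff performing TEA:

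1. A study-team member already at the visit holds the order, opens only that visit's assignment, and sets and operates the TEA device out of view of the staff inflating the balloon.
2. The lab staff who inflate the balloon and record thresholds and VAS are not told the assignment, and use one scripted prompt at every visit.
3. Participants are not told which visit is sham. Sham uses the same electrodes, duration and script, and its settings are written in the protocol.
4. The study-team member handles the comfort adjustment of intensity already planned, with the same scripted comfort check at sham visits, so that the check does not reveal the assignment.
5. Participant and inflating staff each record an active/sham guess at the end of the visit, and the guesses are reported.

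**Cost.** Protocol and CRF wording, and one added CRF question per visit. Device operation moves from the lab staff to the study team, whose role in Section 12 is now CRFs and adherence. Both groups already attend, so no added staff should be needed. Masking will be only partial, because some participants will feel the active site; the recorded guesses will help show how far it failed.

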4.1 Schedule of Events for Each Visit

Every visit is the same and will follow the steps detailed below, with the exception of the first visit which will include the informed consent process. At visit one, the study team will randomly generate the stimulations schedule unique to each study participant; this is the order of locations and currents by using a random generator. For example, ST36-100Hz, ST36-25Hz, PC6-100Hz, PC6-25Hz and Sham-TEA.

48 Hours prior to the visit: The study participants will not take any medications known to affect the gut or pain perception.

8:00 pm on the night before the visit: The study participants begin fasting for their visit the next day. Study participants can still drink water. Study participants cannot drink coffee, tea, juices or eat any food items.

Day of the Visit:

Study participants will come to the study location, the Gastrointestinal Physiology Lab in University of Michigan. The visit will take place in one of the private rooms within the lab. **If the study participant is a women of child bearing potential:** She will complete a pregnancy test provided by the study team. If her pregnancy test is positive, she will be excluded from further participation in the study and will not complete the visit.

Rome IV Criteria for Irritable Bowel Syndrome: Upon arrival for every visit, the study participant will complete the Rome IV Criteria for Irritable Bowel Syndrome survey.

Enema: The study participant will be given a rectal enema to clean the rectum. Then the study participant will undress from the bottom down and be given a gown and sheets for comfort and privacy.

Position the study participant: The study participant will be asked to lie down on the medical examination table on one side and bring his or her knees up to the chest, similar to the fetal position. The table has rails that will protect the study participant from falling. The staff may use pillows to adjust and secure the study participant as well as for comfort.

Electrode Placement: The GI physiology laboratory staff will place two electrocardiogram (ECG) electrodes from of the TEA device on the subject's skin, one on the wrists at location PC6 and the other

Fig.1: Locations of PC6 and ST36.

on upper leg below the knee at location ST36. These two electrodes will be used for delivering weak electrical current stimulation. The electric current and stimulating electrode location is determined by that study participant's randomized stimulation schedule. Electrodes will be placed at both locations at each visit.

An additional three ECG electrodes connected to the ECG machine will be placed on the study participant's skin, one on the manubrium of sternum, one above the breastbone and one on the study participant's right chest. These three electrodes will be used for recording the ECG. Before the placement of each of the 5 electrodes, the skin area where the electrodes to be placed will be carefully cleaned using skin-prep materials.

[figure not shown]

Fig.2: Locations of ECG electrodes to read electrocardiogram.

Baseline data collection with the Barostat:

The Barostat is an FDA-Approved device that measures pressure in the rectum. The device has a thin and flexible polyvinyl catheter (PVC) will be placed 5-15 cm into the study participant's rectum. Once placed, this catheter will be in the rectum for the remainder of the visit.

Rest - 15 Minutes

While the study participant is at rest, baseline data will be collected for 15 minutes.

Inflation with the Barostat:

The GI physiology lab staff will inflate a small balloon at the tip of the catheter and ask the study participant to assess the sensation. During this period, the study participant will be asked to take a note of their first sensation, urge to defecate and maximum tolerance; meanwhile, the study participant will also be asked to report the scale of pain or discomfort during the process of the balloon distention. The study participant will complete the Visual analog Scale Pain Score during inflation.

Maximum Tolerance:

Once the maximum tolerance is reached, the inflation will stop and the air will be removed.

TEA – 15 minutes

One of the randomly assigned TEA methods (or sham-TEA) will be performed for 15 minutes.

Inflation with the Barostat and TEA:

Then the inflation process described above will be repeated while applying the TEA. The study participant may sense the weak electrical stimulation. If the stimulation intensity is uncomfortable for the study participant, the stimulation will be set a level where the study participant feels comfortable. This will be noted in the visit summary. The study participant will complete the Visual Analog Scale Pain Score during inflation.

During the entire period, the ECG signal will be recorded from the three chest ECG electrodes. Once the inflation with barostat and TEA is completed, the study participant's visit will end.

5 Study Enrollment and Withdrawal

Eligibility Criteria:

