5.4 Treatment Assignment Procedures

5.4.1 Randomization Procedures

Prior to the first visit, the order of TEA stimulation at the visits will be randomly assigned to each study participant. Every study participant will undergo every TEA combination (For example, ST36-100Hz, ST36-25Hz, PC6-100Hz, PC6-25Hz and Sham-TEA).

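### The study team generates and holds each participant's five-condition order, with no concealment described, so the pre-TEA reading in the primary outcome is open to condition-dependent bias

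*Combined protocol and SAP*

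**What the plan says.** Three places bear on who knows the schedule, and when.

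- Section 4.1: "At visit one, the study team will randomly generate the stimulations schedule unique to each study participant". This is the whole order of five conditions, not one visit's assignment.
- Section 5.4.1 gives another time: "Prior to the first visit, the order of TEA stimulation at the visits will be randomly assigned to each study participant".
- Section 12: "The study team will be present for each visit and follow the visit CRFs". The same section has the team go through the procedures with the GI physiology lab staff.

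Within a visit, section 4.1 runs in this order: electrodes, 15 minutes of rest, first inflation to maximum tolerance, 15 minutes of TEA or sham, second inflation under TEA. The electrode step already refers to the schedule ("The electric current and stimulating electrode location is determined by that study participant's randomized stimulation schedule"), but it also says: "Electrodes will be placed at both locations at each visit".

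The lab staff take the reading: "The GI physiology lab staff will inflate a small balloon at the tip of the catheter and ask the study participant to assess the sensation". The endpoint is the participant's report: "the study participant will be asked to take a note of their first sensation, urge to defecate and maximum tolerance". Section 3.2.1 takes the visit's first maximum tolerance as the reference for the primary outcome: "This will be defined by comparing their maximum tolerance pre and post TEA".

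The available text names no independent holder of the list, no release of assignments visit by visit, and no masking of the team, the lab staff or the participant. The contents list shows no such subsection under 5.4. Two parts of the document were removed before review, so this absence is judged on the rest.

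**The concern.** The pre-TEA reading should not depend on the condition that follows it. Here it is subjective, it is elicited by staff, and it is taken with a team in attendance that can know what comes next. Slightly earlier stopping or different prompting before a session expected to work would lower the recorded baseline and enlarge the apparent rise.

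Randomising the order does not remove this, because the shift follows the condition and not the visit number. A good sham does not remove it either, since a sham protects only what happens once stimulation starts.

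Two comparisons are exposed in different ways. A shift shared by all active sessions biases active versus sham. A shift tied to one favoured modality biases the ranking of the four modalities, and section 10.2 says the findings will decide which treatment goes into a future trial. Knowing later assignments could also colour booking within the 1 to 3 week window and decisions to end or cancel sessions (section 10.2.1).

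**Working it through.** **Inputs from the documents.** Five conditions, each given once (5.4.1). 25 enrolled for 20 completers at 20% dropout (10.2); this reproduces: 20 / (1 − 0.20) = 25. Section 10.2 says no preliminary data were available, and the plan gives no SD, effect size or power.

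**When the condition can be known to the team.** Under either timing the schedule exists before visits 2 to 5: 25 × 4 = 100 of 25 × 5 = 125 planned visits, or 80 of 100 for 20 completers. At visit 1 it certainly exists beforehand only under 5.4.1, because 4.1 does not place generation before or after that visit's first inflation.

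**How a shift enters the outcome.** Let P be the pre-TEA reading and T the reading under TEA. The change is T − P. If P is recorded lower by b before a given condition and T is unaffected, the change becomes T − (P − b) = (T − P) + b, so the estimated effect of that condition moves by the full b. Adjusting for P with slope β would still leave βb.

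**Illustrative size.** Assumptions, none from the documents: reading SD = 1, correlation ρ between P and T of 0.6 to 0.8, independent changes across visits, no true effect, n = 20, two-sided 5%.

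- SD of one change: √(2(1 − ρ)).
- SD of the difference between two changes: √2 × √(2(1 − ρ)).
- Noncentrality: b√20 / SD of difference. For example, with ρ = 0.7 and b = 0.2: 0.2 × 4.472 / 1.095 = 0.816.

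Unadjusted paired t-test, 19 df (critical value 2.093), one active session versus sham:

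| ρ | SD of difference | b = 0.1 | b = 0.2 | b = 0.3 |
|---|---|---|---|---|
| 0.6 | 1.265 | 6.3% | 10.3% | 17.2% |
| 0.7 | 1.095 | 6.7% | 12.1% | 21.4% |
| 0.8 | 0.894 | 7.6% | 15.8% | 29.7% |

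Tukey-adjusted, five conditions, (5 − 1)(20 − 1) = 76 df, critical value 3.952 / √2 = 2.794, rate per pair (0.7% with no shift):

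| ρ | b = 0.1 | b = 0.2 | b = 0.3 |
|---|---|---|---|
| 0.6 | 1.0% | 2.2% | 4.6% |
| 0.7 | 1.1% | 2.8% | 6.4% |
| 0.8 | 1.4% | 4.1% | 10.5% |

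The same figures apply to one shifted active modality compared with an unshifted one.

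**What concealment would leave.** If the list is closed but earlier conditions are known, the chance of guessing the next one is 1/5, 1/4, 1/3, 1/2 and 1 at visits 1 to 5: 20%, 25%, 33%, 50% and 100%. The mean is 2.283 / 5 = 46%.

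**The case against.** Knowledge of the schedule by the person taking the reading is an inference. Section 4.1 gives the inflation and the questions to the lab staff, section 12 treats them and the study team as separate groups, and nothing says that the staff or the participant see the list. This stands. A reader might infer that every assignment is known at all five visits to whoever takes the reading. The documents support only that the team holding the schedule can know it at visits 2 to 5, and at visit 1 under 5.4.1.

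The direction and size of any shift are conjecture. This also stands: the documents show an unprotected step, not an observed bias. At 0.1 SD the effect on error rates is small.

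The unadjusted active-versus-sham test is not in the plan. Sections 10 and 10.3 specify ANOVA, with Tukey's test between points and between parameter sets, and section 10.2.2 disclaims efficacy. So 10-16% and 17-30% should not be read as error rates of the planned analysis; the Tukey figures are nearer to it. A shift common to all active sessions cancels in active-versus-active comparisons, so the ranking is at risk only from a modality-specific shift. Neither point removes the bias in the estimate, which moves by b whatever test is used.

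Generating a full crossover order in advance is normal practice. That is correct; the gap is that nothing keeps the order from those at the visit. Every participant is due to receive every condition, so a reading of this as selection bias at enrolment would also be wrong.

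**Conclusion.** The point holds as a risk to measurement. The visit team generates the full order, no concealment is described, and a subjective reading taken before stimulation is half of the primary outcome. Any condition-dependent shift in that reading carries through in full.

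Its size cannot be derived from the documents. Under the assumptions shown, a shift of 0.2 to 0.3 SD raises the unadjusted false-positive rate for one active session versus sham from 5% to between 10% and 30%. The Tukey per-pair rate rises from 0.7% to between 2% and 11%. A 0.1 SD shift gives 6-8% and about 1%.

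The documents do not show that bias will occur, or that the lab staff or participants know the schedule. The change is recommended because it is cheap and the findings will select a treatment for a later trial.

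**What to change.** Amend sections 4.1 and 5.4.1 so that they agree, along these lines:

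- The order list is generated before the first visit by an existing statistician or data manager who takes no part in the visits. The study coordinator would not qualify, since section 14.1 has the coordinator documenting visits.
- It is held in sealed envelopes or a locked file, one assignment per participant per visit.
- Each assignment is opened only after the pre-TEA maximum tolerance, first sensation, urge to defecate and VAS score are written on the CRF. The opening time is recorded.
- Electrodes go on both points at every visit before the assignment is opened. Section 4.1 already has "Electrodes will be placed at both locations at each visit", but its electrode step also cites the schedule, and section 6.1 speaks of two electrodes on the preferred location. These statements must be reconciled for the delayed opening to work.

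**Cost.** A short amendment and 25 × 5 = 125 envelopes or an equivalent file. No added participants, visits or procedures. The device is set during the visit instead of before it.

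**Limit.** Staff who know the earlier sessions could still guess the next condition 46% of the time on average, and with certainty at visit 5. The inflation under TEA is not masked by this change. The protocol should also state whether the lab staff and participants are kept unaware of the condition.
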